12.1.1.2 Treatment-Emergent Adverse Events due to Infusion Related/Anaphylactic Reaction

TEAEs that are checked "Yes" in 'Is this Adverse event classified as an infusion related/anaphylactic reaction (IRR)?' in the 'Adverse Event' page of the eCRF will be considered for this summary.

Table of TEAEs due to IRR will be presented in a similar manner to the tables of TEAEs described in section 12.1.1. TEAEs due to IRR will be listed including the variables detailed in section 12.1 with date/time of Blood Pressure (BP) assessment, Systolic Blood Pressure (SBP) (mmHg), Diastolic Blood Pressure (DBP) (mmHg) and comments except whether the event is classified as a secondary complication (Yes, No).

Also signs and symptoms of IRR will be presented in separate table and listing. The number and percentage of subjects with TEAE due to IRR and the number of events will be presented by actual treatment group and sign and symptom within category. A subject is counted only once if they reported one or more events. The

Statistical Analysis Plan

number of events at each level of summarization will be presented as well. Sign and symptom of IRR information will be listed including the following information from the eCRF: SOC, PT and reported term; Start date/time, End date/time, Category, Signs and Symptoms, and Intensity (Grade 1 (mild), Grade 2 (moderate), Grade 3 (severe), Grade 4 (life-threatening), Grade 5 (death)). In case of 'Other' in eCRF, specified terms of signs and symptoms will be coded according to MedDRA, and SOC and PT will be listed as categories and signs and symptoms, respectively, instead of recorded ones in eCRF. Coded categories and symptoms in [Appendix 14.6](#) will be confirmed during blind DRM.

12.1.2 Treatment-Emergent Serious Adverse Event

TESAEs will be presented in a table in a similar manner to the tables of TEAEs described in section 12.1.1.

12.2 Clinical Laboratory Analyses

Clinical laboratory (hematology, biochemistry, urinalysis) tests will be performed in local laboratories and results will be converted to standard units that are defined as in the sections 12.2.1, and 12.2.2.

Hematology, biochemistry and urinalysis parameters will be labeled with a CTCAE term and grading will be applied to post-baseline values for the parameters where possible according to CTCAE v 4.03. When CTCAE grade is upon clinical input only, the grading will not be applied, but grade require numeric and partial clinical input, grade will be assigned based on the numeric portion only. The CTCAE terms and grades for applicable parameters are listed in [Appendix 14.2.1](#). The CTCAE grades for this analysis will be Grade 1 (Mild), Grade 2 (Moderate), Grade 3 (Severe) and Grade 4 (Life-threatening). The CTCAE Grade 5 (Death) will not be applied in this analysis since death cannot be determined from a numeric laboratory result. If the post-baseline result for a subject does not satisfy any CTCAE grade, it will be classified as "No Grade". If a laboratory parameter value falls within the local normal range, the grade will be classified as "No grade" even if the value has the numeric grade according to CTCAE v 4.03.

If the laboratory parameter value falls in outside the normal range: 'low' or 'high', they will be flagged in each visit. All hematology, biochemistry and numeric urinalysis data will be listed with high and low flags to show if a value is outside the normal range.

The results for all hematology, biochemistry and categorical urinalysis parameters will be categorized into Normal, Abnormal/Not Clinically Significant (NCS) or Abnormal/Clinically Significant (CS) using the local laboratory normal ranges used by study site and provided by local laboratory prior to analysis.

The number and percentage of subjects with a result for each grade will be summarized by CTCAE term, CTCAE grade and actual treatment group. The summary includes only the most severe case during the overall visits.

For the purpose of summarization, numeric laboratory parameters with inequality signs ('<' or '>') will be converted to numeric by removing the inequality sign and keeping only the numeric component of the result (e.g., result of '<2.6' would be converted to numeric '2.6'). The values which are converted to SI unit will be used in the analyses. If the maximum of decimal place for converted parameter is greater than or equal to 3, then the result is presented with 3 decimal places in the listing (but Eosinophil result is presented with 4 decimal places). The decimal places for descriptive statistics are presented based on the presented results in the listings.

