4.3.2 Exclusion Criteria

Subjects who meet any of the following criteria will be excluded from the study:

1. Subject is not likely to complete all required study visits or procedures for any reason, in the opinion of the Investigator.
2. Subject has received a treatment with another investigational medical product or participated in another clinical trial within 30 days (or 5 half-lives, whichever is longer).
3. Subject has previous exposure to any anti-influenza monoclonal antibody therapy including CT-P27 prior to study drug administration.
4. Subject has a history of hypersensitivity to any monoclonal antibody or has a known hypersensitivity to any of the treatment components.
5. Subject is taking antiviral treatment for influenza (e.g., zanamivir, oseltamivir, rimantadine, amantadine, peramivir, or ribavirin) or has a history of using these antivirals within 14 days prior to the administration of study drug.
6. Subject has been immunized against influenza with live attenuated or inactivated virus vaccine within 21 days prior to the administration of study drug.
7. Subject has a medical condition including one or more of the following:
 - a) Positive influenza B or influenza A+B infection.
 - b) History or presence of congestive heart failure with symptoms consistent with New York Heart Association Class III or IV functional status within 12 months prior to study drug administration.
 - c) Presence of clinically significant abnormality on a 12-lead ECG at screening that, in the Investigator's clinical judgment, may compromise the safety of the subject or affect the outcome of the study. These include, but are not limited to, a PR interval >200 msec, a corrected QT interval [QTc] >450 msec for male subjects and >470 msec for female subjects, or any evidence of heart block, right bundle branch block, or left bundle branch block.
 - d) History or presence of any clinical condition or evidence of organ dysfunction that may affect either the subject's ability to participate in the study or the study result, in the opinion of the Investigator.
 - e) Subjects with abnormal liver function values. These will which include aspartate transaminase (AST), alanine transaminase (ALT) or alkaline phosphatase (ALP) $\geq 3 \times$ ULN at screening.
 - f) Subject with abnormal renal function values (serum creatinine $\geq 1.7 \times$ ULN with creatinine clearance level ≤ 75 mL/min at screening).

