2. Hepatitis B surface antigen, Hepatitis B surface antibody, Hepatitis C virus antibody, and HIV will be assessed at screening in all subjects (mandatory). The results of these tests are not intended as eligibility assessments, but collected to provide baseline information.
3. For females of child-bearing potential only.
4. Urine pregnancy test will be performed at screening. If the urine pregnancy test gives equivocal results, a serum pregnancy test will be performed prior to study drug administration. Subjects with a positive test result will be excluded from the study.
5. Clinical laboratory analysis will be performed at screening and on Day 3, Day 8. All clinical laboratory analysis will be performed at the local laboratory. The laboratory tests to be performed are presented in Table 3 of CT-P27 2.2 protocol v5.0.
6. Clinical laboratory results will not be used for assessment of eligibility, but to establish baseline values.
7. Vital sign will be performed at screening, Day 1 (prior to infusion), Day 2 (±4 hours), Day 3 (±4 hours), Day 5 (±4 hours), Day 8 (±4 hours) and Day 110 (±5 days) after the start of the study drug infusion. Blood pressure (sitting) and heart rate will be measured after the subject has rested (sitting quietly) for at least 5 minutes.
8. 12-Lead ECGs will be performed at screening, on Day 8 (±4 hours), and Day 110 (±5 days) (or EOS visit in early termination case).

CONFIDENTIAL

35/62 page

Effective Date: 01-Aug-2018

Statistical Analysis Plan

9. Chest x-rays to evaluate the lower respiratory tract will be performed at screening and if the Investigator considers it is clinically appropriate, chest x-rays to evaluate the lower respiratory tract will be performed during the study.
 10. If symptoms have not relieved up to Day 3, chest x-ray will be performed to determine presence of secondary complications of influenza A infection.
 11. Treatment with study drug must occur no more than 48 hours after the onset of symptoms. If the adjustments of visit schedule is required, additional 12 hours can be allowed (Maximum onset of illness: 60 hours).
 12. PK blood sampling at:
 - Day 1: pre-infusion (within 15 minutes prior to the beginning of study drug infusion), at the end of infusion (within 15 minutes after the end of study drug infusion), and 1 hour (± 15 minutes) after the end of the study drug infusion.
 - Day 2: 24 hours (± 4 hours) after the start of the study drug infusion.

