14.2.1 Laboratory Grades

CTCAE Term	Laboratory Parameter	Level	Grade 1	Grade 2	Grade 3	Grade 4
Anemia	Hemoglobin	Low	<LLN - 10.0 g/dL	<10.0 - 8.0 g/dL	<8.0 g/dL	-
Alanine aminotransferase increased	Alanine Aminotransferase (ALT)	High	>ULN - 3.0 x ULN	>3.0 - 5.0 x ULN	>5.0 - 20.0 x ULN	>20.0 x ULN
Alkaline phosphatase increased	Alkaline phosphatase	High	>ULN - 2.5 x ULN	>2.5 - 5.0 x ULN	>5.0 - 20.0 x ULN	>20.0 x ULN
Aspartate aminotransferase increased	Aspartate Aminotransferase (AST)	High	>ULN - 3.0 x ULN	>3.0 - 5.0 x ULN	>5.0 - 20.0 x ULN	>20.0 x ULN
Blood bilirubin increased	Total Bilirubin	High	>ULN - 1.5 x ULN	>1.5 - 3.0 x ULN	>3.0 - 10.0 x ULN	>10.0 x ULN
Cholesterol high	Cholesterol	High	>ULN - 7.75 mmol/L	>7.75 - 10.34 mmol/L	>10.34 - 12.92 mmol/L	>12.92 mmol/L
CPK increased	Creatine Phosphokinase (CPK)	High	>ULN - 2.5 x ULN	>2.5 x ULN - 5 x ULN	>5 x ULN - 10 x ULN	>10 x ULN
Creatinine increased	Creatinine	High	>1 - 1.5 x baseline; >ULN - 1.5 x ULN	>1.5 - 3.0 x baseline; >1.5 - 3.0 x ULN	>3.0 baseline; >3.0 - 6.0 x ULN	>6.0 x ULN

CONFIDENTIAL

40/62 page

Effective Date: 01-Aug-2018

Statistical Analysis Plan

CTCAE Term	Laboratory Parameter	Level	Grade 1	Grade 2	Grade 3	Grade 4
Hemoglobin increased	Hemoglobin	High	Increase in >0 - 2 gm/dL above ULN or above baseline if baseline is above ULN	Increase in >2 - 4 gm/dL above ULN or above baseline if baseline is above ULN	Increase in >4 gm/dL above ULN or above baseline if baseline is above ULN	-
Hyperglycemia	Glucose	High	Fasting glucose value >ULN - 8.9 mmol/L	Fasting glucose value >8.9 - 13.9 mmol/L	>13.9 - 27.8 mmol/L;	>27.8 mmol/L;
Hyperkalemia	Potassium	High	>ULN - 5.5 mmol/L	>5.5 - 6.0 mmol/L	>6.0 - 7.0 mmol/L	>7.0 mmol/L
Hypernatremia	Sodium	High	>ULN - 150 mmol/L	>150 - 155 mmol/L	>155 - 160 mmol/L;	>160 mmol/L
Hypertriglyceridemia	Triglyceride	High	1.71 mmol/L - 3.42 mmol/L	>3.42 mmol/L - 5.7 mmol/L	>5.7 mmol/L - 11.4 mmol/L	>11.4 mmol/L;
Hyperuricemia	Uric acid	High	>ULN - 10 mg/dL (0.59 mmol/L)	-	-	>0.59 mmol/L;
Hypoalbuminemia	Albumin	Low	<LLN - 30 g/L	<30 - 20 g/L	<20 g/L;	-
Hypoglycemia	Glucose	Low	<LLN - 3.0 mmol/L	<3.0 - 2.2 mmol/L	<2.2 - 1.7 mmol/L	<1.7 mmol/L
Hypokalemia	Potassium	Low	<LLN - 3.0 mmol/L	-	<3.0 - 2.5 mmol/L	<2.5 mmol/L
Hyponatremia	Sodium	Low	<LLN - 130 mmol/L	-	<130 - 120 mmol/L	<120 mmol/L

CONFIDENTIAL

Statistical Analysis Plan

CTCAE Term	Laboratory Parameter	Level	Grade 1	Grade 2	Grade 3	Grade 4

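### The graded laboratory table (SAP 12.2, Table 14.3.4.1) counts worst post-baseline grade with almost no reference to baseline, so no planned table counts subjects whose CTCAE grade increased after infusion

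*SAP*

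**What the plan says.** Three rules in SAP 12.2 define the graded laboratory table (Table 14.3.4.1):

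- Only values after baseline are graded: hematology, biochemistry and "urinalysis parameters will be labeled with a CTCAE term and grading will be applied to post-baseline values for the parameters where possible".
- The layout has no baseline dimension: "The number and percentage of subjects with a result for each grade will be summarized by CTCAE term, CTCAE grade and actual treatment group".
- One grade per subject is kept: "The summary includes only the most severe case during the overall visits".

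A further rule gives no grade to a value inside the local normal range. It does not deal with values that were abnormal before infusion.

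Two terms in Appendix 14.2.1 refer to baseline. Grade 1 creatinine reads ">1 - 1.5 x baseline; >ULN - 1.5 x ULN", and Grade 1 hemoglobin increased reads "Increase in >0 - 2 gm/dL above ULN or above baseline if baseline is above ULN".

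The SAP also plans laboratory displays that do use baseline. These are shift tables in the categories normal, abnormal not clinically significant (NCS) and abnormal clinically significant (CS) (SAP 12.2.1 to 12.2.3), and change-from-baseline tables for hematology, biochemistry and urinalysis (Tables 14.3.4.2, 14.3.4.4 and 14.3.4.6). The calculated absolute lymphocyte count is the exception: SAP 12.2.1 puts it in the listing and the CTCAE table but leaves it out of the hematology summary tables.

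On entry, exclusion 7e in Protocol 4.3.2 ("Subjects with abnormal liver function values") applies from 3 x ULN for AST, ALT and ALP. Footnote 6 of the schedule in SAP 14.1 says: "Clinical laboratory results will not be used for assessment of eligibility, but to establish baseline values".

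**The concern.** A subject whose ALT is Grade 1 at screening and unchanged on Days 3 and 8 is counted in Table 14.3.4.1 exactly like a subject who was normal before infusion and became Grade 1 afterwards. All subjects have acute influenza at screening and the only later laboratory visits are Day 3 and Day 8, so baseline abnormalities that persist are plausible. They add a common background to every arm.

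The study is meant to give safety information for choosing doses in later trials (Protocol 2.2, SAP 1.1). A graded table that cannot separate carried-over from emergent abnormality is a weaker tool for that. It also departs from the SAP's own adverse event rule (SAP 12.1.1), under which a condition present at baseline counts only if it worsens.

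**Working it through.** The plan states no figure on this point, so there is nothing to reproduce. The check is a comparison of passages, followed by an illustration with assumed rates.

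**1. Can a graded abnormality be present at entry?** Compare Protocol 4.3.2 with SAP Appendix 14.2.1:

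- AST and ALT: excluded from 3 x ULN; Grade 1 runs from above ULN to 3.0 x ULN. Grade 1 can be enrolled.
- ALP: excluded from 3 x ULN; Grade 2 starts above 2.5 x ULN. Grade 1, and Grade 2 up to just under 3 x ULN, can be enrolled.
- Creatinine: exclusion 7f needs at least 1.7 x ULN together with clearance of 75 mL/min or less; Grade 2 starts above 1.5 x ULN. Grade 2 can be enrolled.
- CK, lymphocytes and white cells: no numeric limit, although exclusion 14 lets the investigator exclude on laboratory results.

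Footnote 6 conflicts with exclusions 7e, 7f and 14 on whether screening results decide eligibility, and these passages must be reconciled. The answer here is the same on either reading: subjects with gradable baseline values can enter.

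**2. Do the two exceptions remove the problem?** For hemoglobin increased, yes: if baseline is above ULN, the grade is counted from baseline. For creatinine, only in part. The appendix lists a multiple of baseline and a multiple of ULN. Read as alternatives, they still put a subject at 1.6 x ULN both before and after infusion in Grade 2.

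**3. Does another table count grade increases?**

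- Shift tables: ALT moving from Grade 1 to Grade 2, judged NCS both times, shows no shift.
- Change-from-baseline tables: group statistics, not counts of subjects by grade.
- TEAE tables: laboratory results enter only if clinically significant under Protocol 6.2.1, so an increase that meets none of those criteria is not counted.
- Absolute lymphocyte count: no baseline-referenced summary table.

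**4. Size, for illustration.** Assumptions: a share b of each arm has a Grade 1 or higher value at baseline that persists without worsening; among the rest, new onset is p1 = 12% on a CT-P27 dose and p0 = 3% on placebo. The documents give none of these rates. The denominator is all subjects in the arm (SAP 5.1).

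- Planned table, any grade: b + (1 - b)p
- Count of subjects whose grade increased: (1 - b)p
- Difference in both: (1 - b)(p1 - p0)

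| b | Planned table | Ratio | Increased grade | Ratio | Difference, both |
|---|---|---|---|---|---|
| 10% | 20.8% vs 12.7% | 1.64 | 10.8% vs 2.7% | 4.0 | 8.1 points |
| 30% | 38.4% vs 32.1% | 1.20 | 8.4% vs 2.1% | 4.0 | 6.3 points |
| 50% | 56.0% vs 51.5% | 1.09 | 6.0% vs 1.5% | 4.0 | 4.5 points |

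For precision at b = 30%, take the planned 70 and 43 subjects:

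- Planned table: SE = sqrt(0.384 x 0.616/70 + 0.321 x 0.679/43) = 9.2 points
- Increased grade: SE = sqrt(0.084 x 0.916/70 + 0.021 x 0.979/43) = 4.0 points

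The same 6.3-point difference is therefore estimated with more than twice the standard error.

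Other assumed rates behave alike. With 25% against 5% new onset and b = 30%, the planned table gives 47.5% against 33.5%, ratio 1.42 instead of 5.0. If only half of those abnormalities persist, the effective b is 15% and the ratio is 36.25/19.25 = 1.88.

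**The case against.** The strongest reply is that little is lost. Five parts of it deserve an answer.

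- **The difference is intact.** With a background common to all arms, the planned table and a count of increased grades give the same risk difference. This stands. The cost falls on the ratio and on precision.
- **The table is split by grade.** A move from Grade 1 to Grade 3 appears in the Grade 3 row, where Grade 1 background cannot mask it. This stands, and the illustration, which pools Grade 1 and above, overstates the effect for high grades. The low-grade rows remain affected.
- **Other tables use baseline.** A reader might infer that Table 14.3.4.1 is the only graded laboratory summary. It is not. Clinically significant laboratory abnormalities after dosing are TEAEs. They are graded by CTCAE under a new-or-worsened rule and are summarized by intensity, with a separate table for Grade 3 and above (SAP 12.1.1, Table 14.3.1.5). What remains uncovered is an increase in grade that does not meet the clinical significance criteria.
- **The table does not claim to show toxicity.** A reader might infer that pre-infusion abnormalities are presented as drug effects. The table's title refers only to CTCAE grading, and the SAP plans no laboratory test. The table does not call its counts treatment-emergent; it only leaves emergent and carried-over grades unseparated.
- **The rates are invented.** The documents give no baseline abnormality rate, so the range of 10% to 50% is assumption. This stands.

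**Conclusion.** The point holds as a limited defect in one descriptive safety table. For all terms except hemoglobin increased, and apart from the baseline-multiple criterion for creatinine, Table 14.3.4.1 combines abnormalities present before infusion with those that arose or worsened afterwards. No planned table counts subjects whose CTCAE grade increased, and absolute lymphocyte count has no baseline-referenced summary table.

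A reader might go further and infer that the table hides a drug effect. The documents do not support that. Randomization should balance baseline abnormality across arms, the risk difference survives under a common background, and the change-from-baseline tables are not subject to this dilution. The damage is a diluted ratio and a noisier contrast. In the illustration at b = 30%, the ratio is 1.20 instead of 4.0 and the standard error 9.2 points instead of 4.0. Those figures rest on the assumed rates, on equal background in the arms, and on baseline abnormalities persisting without worsening. The true size cannot be derived from the documents.

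The change is worth making because it costs almost nothing, not because the safety evaluation fails without it.

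**What to change.** In SAP 12.2, apply the Appendix 14.2.1 grading to the baseline value as well, wherever the criterion does not itself depend on baseline. For creatinine, that means grading the baseline value on the ULN multiples. Hemoglobin increased can stay as it is, because its grades already allow for a baseline above ULN. State both conventions in a table footnote.

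In Table 14.3.4.1, show for each CTCAE term the baseline grade (including no grade) against the worst post-baseline grade, and add n (%) of subjects whose grade increased from baseline, by actual treatment group. Include absolute lymphocyte count, which would then have its only baseline-referenced summary.

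The cost is a few lines of SAP text, some programming and a wider table. The baseline laboratory values are already collected and converted to standard units. No visit, sample or change in sample size is needed.

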12.2.1 Hematology

The following hematology laboratory tests will be included: White blood cells (WBC) ($10^9/L$), Red blood cells (RBC) ($10^{12}/L$), Hemoglobin (g/dL), Hematocrit (Proportion of 1.0), Platelet ($10^9/L$), Neutrophil (Proportion of 1.0), Lymphocyte (Proportion of 1.0), Monocyte (Proportion of 1.0), Eosinophil (Proportion of 1.0), Basophil (Proportion of 1.0), Absolute Neutrophil Count (ANC) ($10^9/L$). In addition, Absolute Lymphocyte Count (ALC) ($10^9/L$) will be calculated as follows: $[WBC (10^9/L) * Lymphocytes (Proportion of 1.0)]$. It will be presented in the listing with CTCAE grading and summarized in the CTCAE grading table, but will not be included in the hematology summary tables.

Statistical Analysis Plan

All hematology parameters will be summarized by parameter and actual treatment group for all scheduled collection times (Baseline, Day 3, Day 8) using descriptive statistics. Also, the additional shift table regarding the results of normality (Normal, Abnormal/NCS, and Abnormal/CS) will be summarized for all scheduled collection visit. All hematology test result data will be listed for each subject by actual treatment group, visit and individual test results.

12.2.2 Biochemistry

The following chemistry laboratory tests will be included: Albumin (g/L), Alkaline phosphatase (U/L), Alanine Aminotransferase (ALT) (U/L), Aspartate Aminotransferase (AST) (U/L), Blood Urea Nitrogen (BUN) (mmol/L), Chloride (mmol/L), Creatine Kinase (CK) (U/L), CK enzyme subtype ($\mu\text{g/L}$), Troponin ($\mu\text{g/L}$), Serum creatinine ($\mu\text{mol/L}$), Creatinine clearance (mL/min), C-reactive protein (nmol/L), Cholesterol (mmol/L), Glucose (mmol/L), Lactate Dehydrogenase (LDH) (IU/L), Potassium (mmol/L), Sodium (mmol/L), Total bilirubin ($\mu\text{mol/L}$), Direct bilirubin ($\mu\text{mol/L}$), Total protein (g/L), Uric acid (mmol/L), Triglyceride (mmol/L).

Biochemistry results will be presented in tables and listing in a similar manner to the tables and listing of hematology in section 12.2.1. Since relevant assessment for CK enzyme subtype and Troponin are performed only when CK result shows a clinical significance, they will not be summarized in visit based summary tables. Creatinine Clearance will be calculated using Cockcroft-Gault formula: $[(140-\text{Age}) * \text{Weight (in kilograms)} * [0.85 \text{ if Female}]] / [72 * \text{Serum Creatinine (in mg/dL)}]$. The Weight assessed at screening and calculated age using birth date and date of serum creatinine assessed at each visit will be used in the formula. Since the creatinine clearance was calculated using value of serum creatinine, additional normality for the creatinine clearance is not collected, therefore, the information will not be listed and summarized in a shift table.

